## 5. Data Safety and Monitoring

**Data and Safety Monitoring Plan.** Overall internal monitoring of the safety of human subjects will be conducted by PIs. At eligibility screening, those identified with possible clinically significant levels of mental health will be a given list for their nearest mental health service, provided through South Africa's free public health service. This is because this is a prevention study – we offset risk by only including individuals with low levels of depressive symptoms. We screen out those who have progressed to clinically significant ranges. The PIs will oversee monitoring activities. For non-emergency issues, a weekly meeting will be held to address study progress, recruitment and retention, data collection, and other factors related to human subjects and meetings will be held more often if necessary. Emergency protocols will be developed to address serious adverse events and emergency ethical issues should these arise during the intervention or follow-up assessments. Staff will be trained in responses to potential adverse events and given protocol guidelines on how to address these situations. We provide these Standard Operating Protocols or SOPs for review. In cases of adverse events such as identification of depression, suicidal or homicidal ideation, staff will be trained to immediately contact the Project Manager to alert them of the situation. The Project Manager will consult with the PIs to address these issues who are on call at all times during active study recruitment, intervention testing, or assessment. Study staff will be instructed to inform participants they do not have to answer questions that they find too distressing and will be reminded that they can discontinue participation at any time. If needed, participants will be linked to services for stabilization and referral process if they decompensate during eligibility screening, intervention testing, or assessment procedures. Moreover, participants who report significant depression or suicide will not be enrolled in the study (per our exclusion criteria) and will be immediately referred for evaluation and if necessary, psychiatric admission at a local emergency department. Moreover, the Project Manager and PIs should be immediately notified. Participants who develop or report significant depression, suicidal, or homicidal risk during the course of experimental intervention or during assessments will be discontinued and immediately referred for evaluation for psychiatric admission at a local emergency department. All adverse events will be immediately reported to PIs. Serious adverse events will be reported to Brown University IRB/University of Cape Town HREC. A written report will also be given in writing to NIH. All ethical issues will be reported in an annual report to Brown University, University of Cape Town, and NIH.

## 6. Data Analyses

**Planned Analyses.** We define primary and secondary outcomes, referring back to the study questions.

**Question 1:** Is this intervention efficacious? That is, is there evidence of hypothesized effects of the intervention, that the intervention will reduce or maintain symptoms that fall below the clinically significant range for depression and reduce or delay actual or intended sexual risk behavior in adolescents?

[figure not shown]
**Analysis plan for Aim 1.** We will compare primary outcomes between the two study arms, at 6- and 12-months versus baseline to quantify the intervention's short- and long-term effects. We will compare the continuous and count outcomes (e.g. CES-DC measurement, # of sexual partners, # of sexual episodes without condom) using student's t-test or Wilcoxon rank-sum test (if normality assumption not satisfied), and categorical outcomes (e.g. chlamydia/gonorrhea infection, any STI, frequency of condom use, ever unprotected sex) using Chi-square test or Fisher's exact test (if frequencies are sparse). Changes of outcomes from baseline will be tested using paired t-test, signed rank-rank test, or McNemar's test, whichever is appropriate. For those who are sexually inactive at study enrollment, their sexual debut time will be summarized by Kaplan-Meier curves, and compared using log-rank test. Given that the study has multiple visits, we will use a unified longitudinal model to estimate and draw inference about intervention effects for the primary outcomes. Model (1) is:  $h\{E(Y_{ij})\} = \alpha_i + \beta_1 R_i + \beta_2 R_i \times Time_j + \beta_3 X_i$ , where  $Y_{ij}$  is the outcome at the  $j$ th visit for the  $i$ th individual,  $h(\cdot)$  is a link function,  $\alpha_i$  is a random intercept capturing within-person effect,  $R_i$  represents the treatment group membership,  $Time_j$  codes the study visit, and  $X_i$  denotes baseline covariates. Hence, coefficients  $\beta_1$  and  $\beta_2$  represent the difference between the intervention and control and the effect interaction with time; estimation of the two parameters will be our primary interest. Depending on distribution of primary outcomes, we will choose an appropriate link function for Model (1), e.g. an identity link for CES-DC score, log link for # of unprotected sex, and logit link for any STI. As a result, the interpretation of  $\beta$ s will be mean difference, log(risk ratio), or log(odds ratio). We will compare key baseline variables (e.g. age, gender, socio-economic status) between arms to ensure balance of randomization, and make adjustments in the model (by adding the term  $\beta_3 X_i$ ) to estimate treatment effects as needed. Model (1) will be fit using generalized estimating equations to account for repeated measures. For time-to-sexual debut, we will fit a Cox model among those who are sexually inactive at baseline; Model (2) is:  $\lambda(t; X_i) = \lambda_{0k}(t) \exp(\beta_1 R_i + \beta_3 X_i)$ , where  $\lambda(t; X_i)$  is the hazard of having sexual debut at time  $t$  for the  $i$ th individual and  $\lambda_{0k}(t)$  is the baseline hazard. In this model,  $\beta_1$  is the log(hazard ratio) that captures distributional difference in sexual debut time between study arms. Because time to sexual debut will differ by age, we will fit a stratified Cox model by grouping participants by enrollment age ( $k = 1, 2, 3$  for age=14, 15, and 16) and assuming difference baseline hazard function  $\lambda_{0k}(t)$  for each group. Model (2) will be fit using the partial-likelihood.

**Question 2:** What mediates and moderates the effect of the intervention on the main outcomes?

Figure 2. Causal pathway illustrating the hypothesized relationships between intervention (I), intermediate factors (IF) and outcomes.

**Mediation Analysis.** We will investigate theoretically-derived mediators proposed to explain the efficacy of *Our Family Our Future* on prevention of HIV/STI acquisition, reducing HIV/STI risk behavior, and reductions in depressive symptoms. Specifically, we examine whether the extent of impact of *Our Family Our Future* on outcomes is mediated by changes in resilience; behavioral skills and efficacy (e.g., condom use, sex refusal); norms and attitudes relating to sex, condom use, gender; family interactions; and social support. Let us denote these potential mediators as intermediate factors (IF).

Our hypothesis is that beside a direct effect on the primary outcome, the intervention can cause changes in these IF at 6-months, which ultimately lead to change in primary outcomes at 12-months. Figure 2 depicts three candidate submodels, using directed acyclic graphs, to represent hypothesized causal pathway leading from intervention to primary outcomes. The full mediation model is given in Figure 2(c), which fully decomposes the effect of the intervention, but contains multiple pathways whose effects are not simultaneously estimable from a single regression model. We will proceed by fitting the following submodels, which we expect will indicate the role of mediators in explaining the effect of our intervention. The time ordering of data collection gives us an excellent opportunity to untangle relationships using causal mediation analysis. Submodel (a) describes the causal effects on intervention on the IF and primary outcomes. Given the study intervention is randomized, this submodel is identified by data. Submodel (b) focuses on the causal effects on intervention and IF on the primary outcomes. The effect of IF in Submodel (b) is subject to confounding, and hence its estimation will be based on certain model assumptions (e.g. sequential ignorability). Estimates of submodels (a) and (b) will generate a rough idea of the relative degree to which intervention effect is mediated by each of IF. If the two models suggest a causal relationship between intervention and an IF and between IF and primary outcomes, its mediation effect will be considered in the full model (c) that describes the full process. Thus from analyses of submodels (a) and (b), we will select the best candidate variables with the strongest mediation effects from intervention to IF, and from IF to the outcome. Statistical modeling will utilize causal mediation models, fit using a weighted two-stage regression approach implemented with SAS macros to estimate the full model (c). For our mediation analysis, we will focus on direct and indirection *natural* effects.

**Moderation Analysis.** We investigate theoretically-derived moderators that may explain responsiveness to *Our Family Our Future* on primary outcomes. Specifically we examine whether the extent of impact of the intervention on outcomes is moderated by the effect of sociodemographics (e.g., gender); severity of parental depressive symptoms, family HIV and orphanhood; structural disparities (e.g., food insecurity); and social protections (e.g., government grants). We will build our moderation analysis around Models (1) and (2) to quantify the moderation effect of these potential factors on the intervention. Specifically, we will add to the two models: their main effects  $\beta_3 M_i$  as well as their interactions with the study intervention  $\beta_4 M_i R_i$ , where  $M_i$  denotes the above potential effect moderators at baseline. Our interest is the interaction coefficients  $\beta_4$ , which capture the differential effect of our intervention on the outcome across levels of each of the potential moderators. We recognize possible *limitations*. For mediation analysis, we use a causal inference method based on a potential outcomes framework which

assumes there is no existing unmeasured confounding. Sensitivity analyses will be conducted to examine if assumptions are valid. Our causal pathway includes multiple mediators, for which statistical methods are limited but being developed. For moderation analysis, we may not have adequate power to detect all (three ways or higher) interactions between interventions and baseline moderators. However, we expect our approach to provide a foundation for future confirmatory analyses.

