## 2. Study design

**Summary of scientific design.** We test the efficacy of *Our Family Our Future* in a 2-arm, single blinded RCT with 6- and 12-month follow-ups. Participants include a sample of N=880 adolescents 14-16 years (and 880 parents) who will be randomized based on permuted blocked randomization (balancing by gender) to an intervention arm (n=440 adolescents and their parents testing *Our Family Our Future*) or a control arm (n=440 adolescents and their parents) of usual care. Study design carefully adheres to elements outlined in the Consolidated Standards of Reporting Trials (CONSORT) Statement. This pilot study adheres to a single blind, randomized pilot trial design with the end goal of informing a full-powered RCT corresponding to a Phase III

---

 The 12-month follow-up with parents and teens may occur up to 24 months afterwards in order to retain as many teen/parent dyads as possible in the longitudinal analysis.

clinical trial. Outcomes will be assessed at baseline, 6 months, and 12 months after the last intervention session. Due to the COVID-19 crisis (March, 2020) we will attempt to first abide by the scheduled 6- and 12-month outcome timepoints for all self-reported and behavioral data with biological data (HIV and STIs) captured when movement restrictions are lifted and/or when physical contact is acceptably safe. If this does not work, we will shift to collecting all 6- and 12-month timepoints for all data to when movement restrictions are lifted and/or physical contact is acceptably safe. The count-down clock for the 6 months and 12 months outcome evaluations will occur after the last intervention session has occurred. Feasibility data and process data on possible mechanisms of change will be collected at eligibility, enrollment, during the intervention sessions, and during baseline and follow-up assessments.

**Study questions.** The primary study questions are:

Question 1: Is this intervention efficacious? That is, is there evidence of hypothesized effects of the intervention, that the intervention will reduce or maintain symptoms that fall below the clinically significant range for depression and reduce or delay actual or intended sexual risk behavior in adolescents?

Question 2: What mediates and moderates the effect of the intervention on the main outcomes?

Question 3: What are the barriers and facilitators of intervention implementation?

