For depressive symptoms, we hypothesize that 25%-35% of participants in the control arm will have a reduced depressive symptom scores (on CES-DC) compared with their baseline score; while about 40-50% participants in the intervention arm will have reduced symptom scores. Table 1 shows the study has a power of >0.80 if the difference between the two study arms is  $\Delta=10\%$  or larger. For HIV/STI acquisition, we power the study based on the outcome of any HIV/STI infection (which we expect to be primarily driven by

change from baseline. Including data from all study visits and adjusting for baseline covariates will potentially increase study power to detect difference between the intervention and control.

**Language.** All study materials and procedures will be conducted in English or isiXhosa. Study materials will be translated by a professional translator, then back-translated to ensure accuracy. Participants will identify language of preference and multi-lingual research assistants (RAs) will conduct procedures in the preferred language. We draw from our established research networks to hire a team experienced intervention delivery, tracking and tracing, and qualitative research with adolescents and families.

**Site description.** Our trial field site will be at DTHF's Masiphumele community center. This spacious, welcoming facility is ideal for delivery of our interactive family-based intervention, with clinic and lab space to facilitate collection of biosamples for HIV and STIs (for site details, see DTHF's Facilities and Resources). We will move to telephonic delivery of the intervention as an option during the COVID-19 crisis.

**Characteristics of the Study Population.** We aim for an initial sample size of N=880 adolescent-parent dyads (n=880 adolescents and n=880 parents) for the intervention. Participants will be recruited from the community setting (Masiphumele Community Center and surrounding community. This site has high HIV prevalence and are primarily black African (99%) and isiXhosa speakers (96%).

**Inclusion and Exclusion Criteria.** We use the following **eligibility criteria** to recruit families into the intervention. Please note that criteria for inclusion of parents was changed from the original grant submission based on critiques of reviewers and requests from NIH. Now parent inclusion criteria reflect more flexibility.

Adolescent inclusion criteria are:

- 1) 14-16 years;

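### Model (1) has no main effect of visit, so with 0/1 arm coding β₂ is the intervention arm's own change, not the between-arm difference in change

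*Combined protocol and SAP*

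**What the plan says.** The Analysis plan for Aim 1 first lists two-sample, paired and log-rank tests. It then says "we will use a unified longitudinal model to estimate and draw inference about intervention effects for the primary outcomes". The right-hand side of that model, Model (1), is "\alpha_i + \beta_1 R_i + \beta_2 R_i \times Time_j + \beta_3 X_i". Here α_i is a person-level random intercept, Time_j codes the visit and X_i holds baseline covariates. Of the arm variable the plan says only that it "represents the treatment group membership"; no numeric coding is given. β₁ and β₂ are said to "represent the difference between the intervention and control and the effect interaction with time; estimation of the two parameters will be our primary interest", and are to be read as a mean difference, log risk ratio or log odds ratio according to the link. The model is fitted by GEE.

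The plan does not say outright whether the baseline visit is a row of Y. Three statements suggest that it is:

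- The aim of the comparison: "We will compare primary outcomes between the two study arms, at 6- and 12-months versus baseline".
- The Study design section: "Outcomes will be assessed at baseline, 6 months, and 12 months after the last intervention session".
- The sample size section: "Including data from all study visits and adjusting for baseline covariates will potentially increase study power".

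X_i is described as a remedy for imbalance: "We will compare key baseline variables (e.g. age, gender, socio-economic status) between arms to ensure balance of randomization, and make adjustments in the model". The baseline value of the outcome is not among the examples. Moderation Analysis builds on Model (1) and adds only the moderator and its product with arm. No section adds a visit effect.

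**The concern.** Time enters Model (1) only multiplied by arm. The random intercept and X_i are constant over visits, so neither can carry a trend common to both arms. If R is 0 for controls, the model has no parameter through which the control mean can move, and any shared change is attributed to the intervention.

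Nothing in the documents suggests a flat control arm, though they give no size for its change. In the pilot (Background), the intervention arm's CES-DC score fell from 12 to 7 while the arms did not differ. That points to a shared fall, although the pilot was not powered for efficacy. The sample size section points the other way. It expects only 25–35% of controls to have a lower score than at baseline, which for symmetric changes with few ties means that controls worsen on average. Background also expects sexual activity to hold steady or rise with age.

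In the first case Model (1) can create an effect. In the second it can hide one, or give β₂ the sign of worsening when the intervention protects. Question 1 of the trial counts keeping symptoms from rising as success, so the second case matters.

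**Working it through.** **Inputs.** From the plan: 440 per arm less 15% loss = 374; two-sided 5%; three visits coded 0, 1, 2. Assumed, because the documents give neither: SD 5 and within-person correlation 0.4. The plan states no power for Model (1), so there is no figure to reproduce. Table 1 rests on two-proportion calculations at 12 months. With 374 per arm and a continuity correction these give 79.8% (stated 80), 86.9% (86) and 91.6% (91), and they do not involve Model (1).

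**Three readings.** Reading 1: R 0/1, baseline in Y. Reading 2: R 0/1, baseline score in X_i, Y at 6 and 12 months only. Reading 3: R ±0.5, equal arms.

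**Algebra, Reading 1, identity link.** The control mean is a at every visit and the intervention mean is a + β₁ + β₂·Time. Hence:

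- β₂ is the intervention arm's slope.
- β₁ is the intervention arm's fitted baseline minus the control mean over visits.
- β₁ + 2β₂ is the intervention arm's fitted 12-month mean minus the control mean over visits.

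Large-sample GEE check (20,000 per arm, same change 0, −2, −4 in both arms): β₂ = −2.01 and β₁ = +2.03. With a time term added they are −0.02 and +0.04. With a logit link and 15/20/25% in both arms, β₂ = 0.32 and β₁ = −0.35; with a time term, 0.00 and −0.01.

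**(A) No true effect, both arms fall 1 point linearly (0, −0.5, −1).**

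- Reading 1, β₂: value −0.50. The variance of a person's slope is 2·25·(1 − 0.4)/4 = 7.5, so SE = √(7.5/374) = 0.142 and z = 3.53. Rejection is 94%.
- Reading 1, 12-month contrast: −1 − (−0.5) = −0.50. SE = √((22.5 + 15)/374) = 0.317, so z = 1.58. Rejection is 35% (simulation 36%).
- Reading 2, β₂: 6-to-12-month change −0.50. SE = √(30/374) = 0.283. Rejection is 42%.
- Reading 2, contrast: −1 − (−0.75) = −0.25. SE = √((21 + 13.5)/374) = 0.304. Rejection is about 13% (simulation 14%).
- Reading 3, and models with visit terms: 4–6%.

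If the fall is complete by 6 months, simulation gives 94% and 33% under Reading 1 and 4–5% under Reading 2. Over SD 4–10 and correlation 0.2–0.6, Reading 1 gives 32–100% (β₂) and 12–55% (contrast); Reading 2 gives 11–78% and 6–23%. With no shared change every version rejects 4–6%.

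**(B) Table 1's CES-DC row of 30% v 40% reduced.** Assume normally distributed change and a linear path. The SD of change is √30 = 5.48. Mean change is +0.524 × 5.48 = +2.87 for controls and +0.253 × 5.48 = +1.39 for the intervention arm, a true 12-month difference of −1.48.

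| | β₂ | β₂ significant as worsening | 12-month contrast | Power for contrast |
|---|---|---|---|---|
| Reading 1 | +0.70 | 100% | 1.39 − 1.44 = −0.05 | 4% (98% with visit terms) |
| Reading 2 | +0.70 | 69% | 1.39 − 2.15 = −0.77 (unrounded means) | 71% (99% with visit terms) |

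Under Reading 3 contrast power is 99%. With integer ties (means 0.5 lower), Reading 1 gives 88% and power 15%; Reading 2 gives 35% and 84%. For the 30% v 50% row, Reading 1 gives β₂ = 0 (5% rejection) and a contrast of −1.45 instead of −2.87, still detected.

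**(C) STI, logit link, Table 1's 30% v 20% at 12 months, common baseline assumed.** At a 20% baseline the controls run 20, 25, 30%, averaging 25% (odds 0.333), and the intervention arm stays at 20% (odds 0.25). Model (1) gives 0.25/0.333 = 0.75, where the true odds ratio is 0.25/0.429 = 0.58. For baselines of 15, 20 and 25%, Reading 1 gives 0.86, 0.75 and 0.66, with power 16–19%, 51–54% and 84–87% instead of 88–90%. Reading 2 gives 0.69–0.70, 0.64–0.65 and 0.60–0.61, with power 63–64%, 78–80% and 89–90%.

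**The case against.** **Arm coding.** If R is fitted as a categorical factor, arm plus arm × time gives each arm its own time course, and a between-arm contrast taken from that fit is valid (5.2% and 5.8% rejection in case A). With ±0.5 coding and equal arms, a shared trend does not bias β₁ or β₂. Both are possible. But the plan writes a single β₂ and reads the coefficients as mean differences or log ratios, which fits a numeric 0/1 indicator better. Under factor coding the interaction coefficients are still within-arm slopes. Under ±0.5 coding the arms are forced to have opposite slopes, and protection weakens with unequal follow-up: at 418 v 330 and a shared 2-point fall, β₂ rejects 18% and the contrast 10%.

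**Baseline in Y.** Primary interest in β₁ makes more sense if Y is post-baseline, since randomization makes a baseline difference zero in expectation. The HIV/STI aim is also worded as incidence. This keeps Reading 2 alive, and it is why both sets of figures are shown. The fault is smaller there but remains whenever outcomes change between 6 and 12 months.

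**Assumed sizes.** The SD, the correlation, the 1-point fall and the baseline STI rates are not in the documents. Eligibility at CES-DC 6–15 caps the screening SD at 4.5. With a baseline SD of 2.9 the case A figures become 99% and 37%, so the direction does not depend on this. Part (B) is more fragile: if about 20% of scores were exactly unchanged, 40% reduced would describe a flat arm.

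**Safeguards.** The formula may be schematic with a term dropped, since it also pairs a random intercept with GEE. The two-sample and paired tests would reveal a moving control arm. That is true, but the plan assigns inference on the primary outcomes to this model and has no rule for a conflict with the tests beside it.

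**Conclusion.** The concern holds. As printed, and with 0/1 arm coding, Model (1) does not estimate what the plan says β₁ and β₂ represent. How far the inference is distorted depends on how much the control arm changes, on whether baseline is an outcome row, and on an SD and correlation that the documents do not give. The most exposed quantity is β₂ when baseline is in Y; the least exposed case is Reading 2 with change complete by 6 months, where the error rate stays nominal. The error can run either way, creating an effect from a shared fall or cancelling one when controls worsen. Time to debut (log-rank, Cox) and the simple between-arm tests remain valid, so the likely practical result is a primary model that contradicts valid tests reported beside it. The formula should be corrected before it is programmed.

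**What to change.** Replace Model (1) with

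`h{E(Y_ij)} = α_i + γ6·I(6m) + γ12·I(12m) + β1·R_i + δ6·R_i·I(6m) + δ12·R_i·I(12m) + β3·X_i`

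If the baseline score is in X_i and not in Y, keep only the 12-month visit term and its product with arm. Carry the same visit terms into the moderation model. State the coding of R and Time and whether baseline is a row of Y. Name in advance the contrasts to be reported at 6 and 12 months: differences in change (δ6, δ12) or arm differences at the visit (β1 + δ6, β1 + δ12).

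The cost is one corrected formula and a few sentences. No data, visits or participants are added, and Table 1 does not change.

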**Eligibility Assessment, Enrollment, and Randomization.** The study staff will assess *eligibility*. Eligibility for parents and eligibility for adolescents will be individually determined. Eligibility will be auto-calculated using a pre-programmed computerized method using our secure mobile project-dedicated android phones or “survey devices” that are part of our field-based data collection system (see details on SurveyToGo software used for data collection). The survey devices will automatically calculate eligibility based on the inclusion/exclusion criteria outlined above. Final eligibility will be determined by dyadic eligibility (that is both parents and adolescents have to be eligible to be invited to participate in this family-based intervention). Eligible parent-adolescent dyads will be invited to participate in the baseline assessment and attend an enrollment session where randomization will occur. If interested, each individual in the dyad will be go through individualized informed consent and assent processes. After completing baseline data collection, each individual in the dyad will be issued matching “invitation tickets” to attend the enrollment session. Invitation tickets provide participants with date and location of the enrollment session. These invitation tickets also display unique ID numbers to allow us to verify at the enrollment session that we have screened individuals for eligibility (by matching unique ID numbers on the ticket with our data system) and help us ensure scheduling of dyads. Dyads will attend an enrollment session where trained study staff will answer questions about the study. Following this information session, study staff will gather voluntary informed consent and assent forms from interested individuals. If consent and assent are obtained for a complete dyad, trained study staff will use a computerized block randomization procedure using our FileMaker Software which automatically determines dyad assignment to the intervention or control group based on programming out [name] and our data team. The block randomization procedure will balance allocation dyads for adolescent gender. Dyads assigned to the intervention group will receive the first intervention session that same day. Dyads assigned to the control group will be given usual care (consisting of a packet of existing available brochures on HIV, STIs, mental health including places to access care). Because randomization occurs in a group setting, assignment is not concealed from participants or from study staff who are part of the intervention team or fidelity

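### Gender is the blocking factor but is not fixed in the Aim 1 analysis (a small, conservative loss), and the promise to adjust for contamination is not kept out of the primary comparison

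*Combined protocol and SAP*

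**What the plan says.** **Design.** Section 2 (Study design) describes participants "who will be randomized based on permuted blocked randomization (balancing by gender". Section 3 (Eligibility Assessment, Enrollment, and Randomization) confirms it: "The block randomization procedure will balance allocation dyads for adolescent gender".

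**Analysis.** In Section 6, Analysis plan for Aim 1, gender is named once: "We will compare key baseline variables (e.g. age, gender, socio-economic status) between arms to ensure balance of randomization". Adjustment then follows "to estimate treatment effects as needed", with no criterion. The simple comparisons (t-test or Wilcoxon, chi-square or Fisher) are unadjusted. For adolescents sexually inactive at entry, "their sexual debut time will be summarized by Kaplan-Meier curves, and compared using log-rank test", with no strata. Models (1) and (2) each carry a term in X, where X "denotes baseline covariates". Model (2) is stratified by enrolment age and does not name gender. The Moderation Analysis adds gender, but only to study effect modification. The power section remarks that adjusting for baseline covariates may raise power, without naming any.

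**Contamination.** In Section 2, Blinding, control dyads are screened for contamination, which is checked at the 6- and 12-month assessments. The paragraph ends with a commitment to adjust for it when the data are analysed. It gives no method and names no analysis. The Aim 1 plan does not mention contamination; it says "We will compare primary outcomes between the two study arms".

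**The concern.** Two things are left open, and they pull in different directions.

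(a) An analysis should reflect the factor on which allocation was restricted. If gender predicts the outcome and is left out, the reported standard error still contains between-gender variation that blocking has already removed from the arm comparison. The tests are then too cautious. The rule for adding covariates depends on an imbalance that blocking is designed to prevent.

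(b) Contamination is observed after randomisation and is described as screened in control dyads. If it entered the efficacy model as a covariate, the arm coefficient would compare the whole intervention arm with uncontaminated controls, which is not the randomised contrast. Control families who share materials may be at higher or lower risk than others, so the bias has no known sign. Sharing is possible because families of both arms meet at the enrolment session ("Because randomization occurs in a group setting, assignment is not concealed from participants"), but no passage gives a rate.

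**Working it through.** **Inputs from the documents.** 880 adolescents, 440 per arm; two-sided alpha 0.05; 15% loss, so 440 × 0.85 = 374 per arm; half sexually inactive, so 374 × 0.5 = 187 per arm; STI 30% vs 20%; debut 30% vs 17.5%; 56% female (pilot). **Assumed:** block sizes, all gender effects, all contamination inputs.

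**1. The plan's own power.** For STI 30% vs 20% at 374 per arm, the null term is 1.96 × √(2 × 0.25 × 0.75/374) = 0.0621 and the alternative SE is √((0.21 + 0.16)/374) = 0.0315. Power = Φ((0.10 − 0.0621)/0.0315) = 88.6%, or 86.9% with continuity correction (plan: 86%). For debut, HR = ln 0.825/ln 0.70 = 0.539 and events = 187 × 0.475 = 89. Power = Φ(√89 × (1 − 0.539)/(1 + 0.539) − 1.96) ≈ 80.5% (plan: 80%). The inputs are therefore read correctly.

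**2. Can the balance check flag gender?** Take 493 girls and 387 boys, one running list per gender, and each gender's arms differing by half a block in opposite directions. With d = block size/4, chi-square = 2d²(1/246.5 + 1/193.5). Blocks of 4/6/8/10 give p = 0.89/0.84/0.79/0.73. The plan does not say whether blocks restart at each enrolment session; if they do, flagging was still rare, at most about 0.4% in the scenarios tried. In the sexually inactive half, under an assumed p < 0.05 rule, gender was flagged in 0.5% of simulated trials with equal inactivity, 0.9% with 60% of girls and 37% of boys inactive, and 1.1% with 65% and 31%.

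**3. Effect of leaving gender out of single-visit tests.**

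- *Continuous outcome.* After blocking and 15% random loss, true SE = reported SE × √(1 − 0.85R²), where R² is the share of variance due to gender. Size = 2(1 − Φ(1.96/√(1 − 0.85R²))). R² = 0.02/0.05/0.10 gives 4.8/4.5/4.1%. Power without vs with gender, at a nominal 80%: 80.2 vs 80.8, 80.5 vs 82.0, 81.1 vs 84.0, a loss of 0.6/1.5/2.9 points.
- *Any STI, chi-square vs Mantel-Haenszel by gender (simulated).* Gender OR 1.5/2/3 at 25%: size about 4.9/4.8/4.4 to 4.6%. Power at 30% vs 20%: 88.7 vs 88.9, 88.7 vs 89.3, 89.0 vs 90.3. Repeat simulations put the losses at about 0.1 to 0.2, 0.4 to 0.6 and 1.0 to 1.3 points.
- *Debut, log-rank unstratified vs stratified by gender (10,000 simulated trials).* Gender HR 1.5/2/3.14: size 4.8/4.5/4.3%; power 82.1 vs 82.5, 81.8 vs 82.8, 82.2 vs 84.8. Simulation error is about 0.8 points for each power, so the smallest difference is not distinguishable from noise. HR 3.14 = ln(1 − 0.382)/ln(1 − 0.142) comes from the cohort in the Significance section (debut in 38.2% of males and 14.2% of females at age 15). It is an upper case, not a 12-month hazard ratio in this trial.

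A gender effect that is constant over time cancels in change from baseline, and in β₂ with the identity link; the loss there is zero. The STI and continuous figures describe the unadjusted single-visit tests, not Model (1) fitted by GEE.

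**4. Contamination as a covariate.** Assume no true effect, 374 per arm, STI 25%, and 10% of controls contaminated with risk RR times that of other controls. Uncontaminated prevalence = 0.25/(0.9 + 0.1 × RR), compared with 25% in the intervention arm:

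| RR | Apparent OR | Type I error |
|---|---|---|
| 0.5 | 0.93 | 6.9% |
| 0.75 | 0.97 | 5.4% |
| 1 | 1.00 | 5.0% |
| 1.5 | 1.07 | 6.6% |
| 2 | 1.13 | about 11% |

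With 5% contaminated, type I error lies between 5.0 and 6.6%.

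**The case against.** On gender, the plan does foresee covariate adjustment. The power section expects it to help, both models contain a covariate term, and gender is among the three key variables named. The analysts may well include it. That is fair, and it rules out saying that the plan ignores covariates. What stands is that nothing commits the plan to gender, and the stated trigger will almost never fire for it.

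The consequence is also small. The plan places inference for the primary outcomes in the longitudinal model and looks at change from baseline; for the CES-DC score the loss there can be nil. A reader might infer that omitting a blocking factor inflates type I error or invalidates the comparison. The calculations show the opposite direction.

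Enrolment age is not a blocking factor, so the same argument does not require it in Model (1) or in the log-rank strata.

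On contamination, the commitment sits in the Blinding paragraph, whereas the analysis plan compares the randomised arms and defines X as baseline covariates. Intervention families are also asked not to share what they learn. A reader might infer that the primary analysis will be adjusted for contamination. The documents do not say so, and the definition of X speaks against it. The objection leaves standing only that an unqualified promise has no place in the models as written.

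**Conclusion.** Both parts hold as minor points of specification.

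(a) The blocking factor is not fixed in the Aim 1 analysis. Under the assumed gender effects, two-sided size falls to about 4.1 to 4.9%. The power lost is about 0.1 to 1.5 points for weak to moderate effects, up to about 3 for the strongest, and zero where a time-constant gender effect cancels. The documents give no gender effect for STI or CES-DC, so these are ranges, not predictions.

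(b) The Blinding paragraph and the Aim 1 plan need to be reconciled. Type I error of 5 to 11% arises only if contamination is entered as a covariate, at the assumed 10% rate and risk ratios of 0.5 to 2. The upper end needs contaminated controls to carry twice the risk of the others. It illustrates what the open wording would allow and is not an expected error rate for this trial.

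**What to change.** In Section 6, Analysis plan for Aim 1, replace the need-based rule with:

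> *Gender, the blocking factor, is included in Model (1) for every outcome and as a covariate in Model (2), whatever the baseline comparison shows. The log-rank test is stratified by gender. Models (1) and (2) are the primary inference; the unadjusted t-test and chi-square comparisons are descriptive.*

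The last sentence is needed because those unadjusted tests would otherwise stay as they are. Model (2) keeps its stratification by enrolment age.

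In Section 2, Blinding, replace the contamination commitment with:

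> *The primary analysis is by randomised arm without adjustment for contamination; contamination is reported and examined only in a sensitivity analysis.*

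**Cost.** Wording only; gender is already recorded and the sample size is unchanged. OR and HR become conditional on gender, a very small shift. For 30% vs 20%, OR 0.583 becomes 0.581/0.576/0.566 at gender OR 1.5/2/3. For debut 30% vs 17.5%, HR 0.539 becomes 0.538/0.534/0.525 at gender HR 1.5/2/3.14.

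Adding age to Model (1) or to the log-rank strata is optional. Stratifying the log-rank test by both factors costs about 0.7 points of power if neither predicts debut (80.7 vs 81.4%). It gains 1.0 to 3.1 points at gender HR 1.5 to 3.14 with an assumed age HR of 1.5 per year.
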